7.1 Trial Schedule of Events Chart

Trial Period:	Screening Phase	Treatment Cycles			8	Post-Treatment				
Treatment Cycle/Title:	Screening	1	2	3	4	5+	EOT ⁱ	Safety Follow-up 1	Safety Follow-up 2 ^b	Survival Follow-up
Scheduling Window (Days):	-28 to -1		± 7	±7	± 7	± 7	± 7	30 days (+ 2 days) post last treatment or prior to starting new treatment	90 days (+ 7 days) post last treatment	Every 12 weeks (+ 14 days)
CBC with Differential ^g	Х	х	Х	х	Х	х				
Comprehensive Serum Chemistry Panel ^{e & g}	х	x	x	x	x	х				
T3, FT4 and TSH ^g	Х	х		х		xf				
Efficacy Measurements										
Tumor Imaging ^c	х					х	х			
Tumor Biopsies/Archival Tissue Collection/Correlative Studies Blood										
Optional Archival or Newly Obtained Tissue Collection ^d	х							х	x	х
Correlative Studies Blood Collection	х		x		x	x ^j		x ^j		

^a Administered according to schedule outlined in table 2. Vesanoid drug supply will be dispensed in clinic on Cycle 1 Day -1 for Cycle 1, Cycle 1 Day 0 for Cycle 2, Cycle 2 Day 0 for Cycle 3 and Cycle 3 Day 0 for Cycle 4.

^b To be completed only for subjects who have not initiated a new therapy. Can be collected at a regularly scheduled clinic visit or via patient contact by telephone.

^e Tumor imaging generally performed every 12 weeks per standard of care for the clinic and evaluated by RECIST 1.1 criteria (Section 11.3 - *Appendices*). Baseline tumor imaging should be completed within 28 days of starting treatment; however, exceptions may be approved after discussion with the principal investigator. Brain metastases that were radiated prior to starting the trial should be re-imaged at the standard 12 week frequency, or as deemed clinically appropriate, by the treating physician.

^d Optional additional tissue collection will be obtained from archival or future biopsies if available.

^e To include lactate dehydrogenase at screening.

^f To be collected every other cycle per standard of care for clinic.

^g Screening labs should be performed within 10 days of treatment initiation.

^h Within 72 hours prior to receiving the first dose of study medication.

ⁱTo be completed when it is decided that the subject will discontinue study treatment. Tumor imaging is only required at investigator's discretion. This visit can be combined with the first safety follow-up visit if the subject is planning to start a new treatment.

 $j \le 60$ days after last Vesanoid treatment.

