The choice of the 200 mg Q3W as an appropriate dose for the switch to fixed dosing is based on simulations performed using the population PK model of pembrolizumab showing that the fixed dose of 200 mg every 3 weeks will provide exposures that 1) are optimally consistent with those obtained with the 2 mg/kg dose every 3 weeks, 2) will maintain individual patient exposures in the exposure range established in melanoma as associated with maximal efficacy response and 3) will maintain individual patients exposure range established in melanoma that are well tolerated and safe.

A fixed dose regimen will simplify the dosing regimen to be more convenient for physicians and to reduce potential for dosing errors. A fixed dosing scheme will also reduce complexity in the logistical chain at treatment facilities and reduce wastage.

All the patients will receive 200mg Q3W pembrolizumab treatment plus the supplemental treatment of 150 mg/m² VESANOID orally for 3 days surrounding each of the first four infusions of pembrolizumab (day -1, day 0, day +1) for a total of 12 days of VESANOID treatment (Section 2.2 *Trial Schema/Diagram*). The total daily dose of VESANOID may be taken anytime on the day before the pembrolizumab infusion (day -1) according to the patient's preferences, prior to the pembrolizumab infusion on the day of the infusion (day 0), and anytime on the day after the pembrolizumab infusion (day 1) according to the patient's preferences.

VESANOID Dose Selection

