6.1.1.2.3 Dose Modifications for VESANOID

If patients experience grade 3 or 4 toxicity that is believed to be related to the VESANOID, then the VESANOID will be held until the toxicity resolves to grade 0 or 1. In the case where the grade 3 or 4 toxicity is believed to be related to Pembrolizumab, the dose modification guidelines in table 3 will be followed. If the toxicity appears to be related to a combination of Pembrolizumab and VESANOID, the VESANOID will be held and the guidelines in table 3 will be followed. After the toxicity has resolved, the VESANOID will either be restarted at the next scheduled time at a reduced dose of 100mg/m² or will be discontinued for serious toxicities. The decision to discontinue treatment will be based on what the treating physician feels is in the subjects' best interest. If the grade 3 or 4 toxicity returns, the VESANOID will be held indefinitely.

The severity of the adverse events will be rated on a scale of Grade 1-4 and reported according to the Data and Safety Monitoring Plan using CTCAE version 4.0. Medical oncologists at the University of Colorado Hospital Cutaneous Oncology Clinic specialize in melanoma and have extensive experience treating patients with immune-based therapies that cause immune-related adverse events. The Principal Investigator will be notified of all adverse events that occur during this trial and will work with the treating oncology team to determine the likelihood of VESANOID's contribution to the adverse event.

VESANOID Related Toxicity

Significant VESANOID related toxicity is defined as any >= grade 3 nonhematologic toxicity related to VESANOID, > = grade 4 hematologic toxicity related to VESANOID or other grade VESANOID related adverse events that lead to treatment discontinuation. An exception is VESANOID related headache not optimally managed with supportive care therapies [acetaminophen, non-steroidal anti-inflammatory medication, or Imitrex (sumatriptan)] or that does not resolve within 72 hours of stopping the VESANOID. A patient's choice to stop all VESANOID, with or without a dose reduction, due to headache alone will not be considered a dose limiting toxicity.

Dose Limiting Toxicity and Study Discontinuation Criteria

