6.1.2 Timing of Dose Administration

Trial treatment with Pembrolizumab should be administered on Day 0 of each cycle after all procedures/assessments have been completed as detailed on the *Trial Schedule of Events Chart (Section 7.1)*. All trial treatments will be administered on an outpatient basis. VESANOID will be administered on day -1, 0 and 1 with each of the first four cycles of Pembrolizumab. VESANOID will be administered twice a day (75mg/m² each dose for a total dose of 150mg/m²).

Pembrolizumab 200 mg will be administered as a 30-minute IV infusion every 3 weeks. Given the variability of infusion pumps from site to site, a window of -10 minutes and +10 minutes is permitted (i.e., infusion time is 30 minutes: -10 min/+10 min).

The Pharmacy Manual and investigational brochure contains specific instructions for the preparation of the pembrolizumab infusion fluid and administration of infusion solution.

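### In Cycles 2–4 no toxicity check is required before the patient starts pre-dispensed VESANOID on Day -1, so the hold/reduce rule can act one day's dose too late

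*Combined protocol and SAP*

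**What the plan says.** **Dosing and supply.** Table 2 (Section 6.1) puts VESANOID on Days -1, 0 and 1 of the first four cycles. Footnote a of the Section 7.1 chart states: "Vesanoid drug supply will be dispensed in clinic on Cycle 1 Day -1 for Cycle 1, Cycle 1 Day 0 for Cycle 2". It continues the same pattern for Cycles 3 and 4. Cycle 1 therefore has a clinic contact on Day -1, and Cycles 2–4 have none.

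**Timing of the capsules.** Under Section 4.2.2 the Day -1 dose "may be taken anytime on the day before the pembrolizumab infusion (day -1"), as the patient prefers. The Day 0 dose is to come "prior to the pembrolizumab infusion on the day of the infusion (day 0"), and that section speaks of the whole day's dose. Section 6.1.2 instead says "VESANOID will be administered twice a day", in two doses of 75 mg/m².

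**The gate.** Section 6.1.2 says: "Trial treatment with Pembrolizumab should be administered on Day 0 of each cycle after all procedures/assessments have been completed". There is no matching sentence for VESANOID. The chart marks adverse-event review, CBC and chemistry once per cycle, in columns headed by cycle rather than day, with a window of ±7 days from Cycle 2 on.

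**The rule the gate should serve.** Section 6.1.1.2.3 says that for grade 3–4 toxicity believed related to VESANOID, "then the VESANOID will be held until the toxicity resolves to grade 0 or 1". It adds: "If the toxicity appears to be related to a combination of Pembrolizumab and VESANOID, the VESANOID will be held". After resolution, "the VESANOID will either be restarted at the next scheduled time at a reduced dose" of 100 mg/m², or it is discontinued.

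**The concern.** A hold rule works only if someone knows about the toxicity before the next dose. In Cycles 2–4 the patient has the capsules at home and may start them on Day -1, fully in compliance, with no adverse-event or laboratory review required since the previous cycle's visit. The patients at issue are those with related grade 3–4 toxicity that they have not mentioned, or that shows only in blood tests. An example is a transaminase or bilirubin rise attributed to the combination. Such a patient could restart at the unreduced dose when the protocol calls for a hold or a reduction.

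Section 4.2.2 explains that the de-escalation design was chosen because of concern about the toxicity of short courses at this high dose. A check before each unsupervised restart serves the same purpose.

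**Working it through.** The point is about the order of events, so there is no figure in the plan to reproduce. The check has three parts.

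**1. Does any text require an adverse-event or laboratory review before Day -1 of Cycles 2–4?**

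- Section 6.1.2: assessments must be complete before pembrolizumab on Day 0. It does not mention Day -1.
- Section 7.1 chart: one review per cycle, no day given. The ±7-day window permits a review on or before Day -1 but does not require it.
- Section 7.1 footnote g: sets a laboratory deadline for screening only.
- Sections 7.2 and 7.2.2.1: extra evaluations when clinically needed, which presupposes a signal.
- Section 10.3.1: toxicity is handled in real time once known. No patient contact is scheduled.
- Sections 7.2.2.4 and 7.2.2.5: vital signs and ECOG status before each dose of trial treatment. Table 2 and Section 7.2.7.3.1 count VESANOID as trial treatment. These are not adverse-event or laboratory reviews, carry no hold threshold, and have no Day -1 contact in Cycles 2–4 at which to be done.
- Section 7.2.2.3: a directed examination before treatment, as clinically indicated.

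None of these requires the review. Nor does any text place the Day 0 VESANOID after the Day 0 assessments. Section 4.2.2 places it only before the infusion.

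**2. Intervals (three-week cycle, so the next Day 0 is Day 21 and the next Day -1 is Day 20).**

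- Last required review (Day 0) to the next Day -1: 21 − 1 = 20 days. With one visit moved by ±7 days the range is 13 to 27.
- Last VESANOID dose (Day 1) to the next Day -1: 20 − 1 = 19 days.

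The last required review also precedes that cycle's infusion and its Day 1 VESANOID, so it cannot show what they cause.

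**3. Dose taken before required review, per course.**

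| Situation | Dose before review | Share of course |
|---|---|---|
| Day -1 only, 150 mg/m² level | 150 of 3 × 150 = 450 mg/m² | 33% |
| Day -1 only, 100 mg/m² level | 100 of 3 × 100 = 300 mg/m² | 33% |
| Conditional: first Day 0 half-dose also taken before assessments (150 level) | 150 + 75 = 225 mg/m² | 50% |
| Conditional: whole Day 0 dose also taken before assessments (150 level) | 150 + 150 = 300 mg/m² | 67% |

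The first two rows follow from the schedule. The last two need an extra condition that the protocol allows but does not state.

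- If a hold was due, the Day -1 excess is the whole dose: 150 mg/m², or 100 mg/m² at the reduced level.
- If the toxicity had resolved and a reduced restart was due, the Day -1 excess is 150 − 100 = 50 mg/m².
- Day -1 doses in Cycles 2–4 make up 3 of the 4 × 3 = 12 VESANOID days per patient (25%). This counts dosing days, not patients at risk.

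The documents give no rate of unreported or laboratory-only toxicity, so no number of affected patients can be computed.

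**The case against.** The case on the other side is substantial, and much of it stands.

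- **Known toxicity is covered.** The hold in Section 6.1.1.2.3 is tied to no visit, so anything the patient reports or an unscheduled test shows can trigger it at once. Symptomatic grade 3–4 events are likely to be reported.
- **There is a long drug-free interval.** Section 4.2.2 reports that common ATRA effects in an earlier trial, and headache in the team's own ipilimumab trial, resolved when the drug was stopped. After about 19 days off VESANOID, toxicity from that drug alone is less likely to be active. Immune-related or combination toxicity may persist, so the risk is not zero.
- **Known liver abnormalities are partly handled.** Table 3 withholds pembrolizumab at grade 2 and suggests liver tests weekly or more often. VESANOID is scheduled around infusions, so a known withhold ordinarily leaves no infusion to dose around. A compulsory extra draw after an earlier abnormality would largely repeat this advice and is not proposed.
- **A call cannot find a first toxicity that shows only in blood tests.** This is correct.
- **The pre-dose vital signs and ECOG might imply a Day -1 contact.** If so, the text conflicts with take-home dosing and needs clarifying anyway.

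These points shrink the exposure. They do not supply the missing requirement. A reader might infer that half or two-thirds of every course is taken unchecked. The documents do not support that, because it depends on Day 0 capsules being taken before that day's assessments. The two-thirds figure also prefers the rationale's wording in Section 4.2.2 to the twice-daily instruction in Section 6.1.2.

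**Conclusion.** The gap is real and narrow. In Cycles 2–4 the hold/reduce rule has no required check before the Day -1 VESANOID dose, and the Day 0 dose is not required to follow the Day 0 assessments. The supported size is one day's dose per course: 150 mg/m², or 100 mg/m² at the reduced level. Day 0 capsules add to this only if taken before the review. Once toxicity is found on Day 0, the rest of the course can be stopped or reduced.

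The patients concerned have related grade 3–4 toxicity that is unreported or silent and either still active after about 19 days off VESANOID, or resolved but calling for a reduced dose. A reader might also infer that between-visit toxicity goes unmanaged, or that patients will probably be harmed. Neither follows: reported toxicity is covered, and the number affected cannot be estimated.

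The conclusion assumes the nominal three-week schedule and assessments done at the Day 0 visit. The consent pages are not in the public document, so an instruction there to wait for clearance cannot be excluded. The change is worth making because it is cheap and lets the protocol's own rule act in time.

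**What to change.** Amend Section 6.1.2 and footnote a of the Section 7.1 chart.

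1. Before the Day -1 dose of each of Cycles 2–4, require a short documented adverse-event call against the Section 6.1.1.2.3 criteria, with review of any laboratory results available. Tell patients not to start the pre-dispensed capsules until the site confirms the go-ahead and the dose.
2. Require the Day 0 VESANOID to be taken after the Day 0 adverse-event and laboratory review. Reconcile Section 4.2.2 (whole day's dose before the infusion) with Section 6.1.2 (two doses a day).

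Cost: protocol wording, a patient instruction and 3 calls per patient, so at most 24 × 3 = 72 short calls if all 24 patients complete four courses. No new tests or staff are needed.

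Limit: a first toxicity visible only in blood tests would still be found on Day 0. Step 2 confines that case to the Day -1 dose.

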7.2 Trial Procedures

Section 7.1 - The *Trial Schedule of Events Chart* - summarizes the trial procedures to be performed at each visit. Individual trial procedures are described in detail below. It may be

necessary to perform these procedures at unscheduled time points if deemed clinically necessary by the investigator.

Furthermore, additional evaluations/testing may be deemed necessary by the Sponsor/Principal-Investigator or treating physician for reasons related to subject safety. In some cases, such evaluation/testing may be potentially sensitive in nature (e.g., HIV, Hepatitis C, etc.), and thus local regulations may require that additional informed consent be obtained from the subject. In these cases, such evaluations/testing will be performed in accordance with those regulations.

All trial procedures will be performed by the investigator, or a qualified designee (also an IRB approved research personnel for the study).

7.2.1 Administrative Procedures

7.2.1.1 Informed Consent

All subjects must first read, understand, and sign the IRB-approved informed consent form (ICF) before any study-specific screening procedures are performed. After signing the ICF, completing all screening procedures, and being deemed eligible for entry, subjects will be enrolled in the study.

7.2.1.2 Inclusion/Exclusion Criteria

All inclusion and exclusion criteria will be reviewed to ensure that the subject qualifies for the trial.

7.2.1.3 Medical History

A medical history will be obtained and will include all active conditions, and any condition diagnosed within the prior 10 years that are considered to be clinically significant by the investigator. Details regarding the disease for which the subject has enrolled in this study will be recorded separately and not listed as medical history.

7.2.1.4 Prior Medications

Prior medication taken by the subject within 28 days before the first dose of trial treatment, including any protocol-specified washout requirement, will be reviewed and recorded. Treatment for the disease for which the subject has enrolled in this study will be recorded separately and not listed as a prior medication.

7.2.1.5 Concomitant Medications

Medication, if any, taken by the subject during the trial will be recorded. All medications related to reportable SAEs and ECIs should be recorded as defined in Section 6.2 (*Concomitant Medications/Vaccines (allowed & prohibited*)).

7.2.1.6 Disease Details and Treatments

7.2.1.6.1 Disease Details

Prior and current details regarding disease status will be obtained.

7.2.1.6.2 Prior Treatment Details

All prior cancer treatments including systemic treatments, radiation and surgeries will be reviewed.

7.2.1.6.3 Subsequent Anti-Cancer Therapy Status

All new anti-neoplastic therapy initiated after the last dose of trial treatment will be reviewed. If a subject initiates a new anti-cancer therapy within 30 days after the last dose of trial treatment, the 30-day Safety Follow-up visit must occur before the first dose of the new therapy. Once new anti-cancer therapy has been initiated, the subject will move into survival follow-up.

7.2.2 Clinical Procedures / Assessments

7.2.2.1 Adverse Event (AE) Monitoring

Each subject will be assessed to evaluate for potential new or worsening AEs as specified in the *Trial Schedule of Events Chart (Section 7.1)* and more frequently if clinically indicated. Adverse experiences will be graded and recorded throughout the study and during the follow-up period according to NCI CTCAE Version 4.0 (see Section 11.2 - *Appendices*). Toxicities will be characterized in terms regarding seriousness, causality, toxicity grading, and action taken with regard to trial treatment.

Please refer to section 7.3 (Adverse Events (AE) – Assessment, Recording and Reporting) for detailed information regarding the assessment and recording of AEs.

7.2.2.2 Full Physical Exam

The investigator or qualified designee will perform a complete physical exam during the screening period. Clinically significant abnormal findings should be recorded as medical history. A full physical exam should be performed during screening,

7.2.2.3 Directed Physical Exam

For cycles that do not require a full physical exam per the *Trial Schedule of Events Chart (Section 7.1)*, the investigator or qualified designee will perform a directed physical exam as clinically indicated prior to trial treatment administration.

7.2.2.4 Vital Signs

The investigator or qualified designee will take vital signs at screening, prior to the administration of each dose of trial treatment and at treatment discontinuation as

specified in the *Trial Schedule of Events Chart (Section 7.1)*. Vital signs should include weight and other vital signs per standard of care.

7.2.2.5 Eastern Cooperative Oncology Group (ECOG) Performance Scale

The investigator or qualified designee will assess ECOG status at screening, prior to the administration of each dose of trial treatment and discontinuation of trial treatment as specified in the *Trial Schedule of Events Chart (Section 7.1)*.

7.2.3 Efficacy Measurement

7.2.3.1 Tumor Imaging and Assessment of Disease

Following the standard of care for pembrolizumab treatment, imaging will be performed at the treating physician's discretion. The imaging will be reviewed by the investigator according to the RECIST criteria (version 1.1), to monitor the appearance of new metastatic lesions and the size of existing lesions.

7.2.4 Tumor Tissue Collection and Correlative Studies Blood Sampling

Plasma will be banked from every patient for cytokine analysis, potential biomarker and other correlative studies. Plasma will also be collected for potential analysis of plasma VESANOID levels in the event this could correlate with results from the immunologic analysis. Whenever possible, tumor samples will be cataloged and stored at the CU Melanoma Biorepository. Additional correlative studies may include genomic analysis.

7.2.5 Laboratory Procedures/Assessments

7.2.5.1 Standard safety laboratory tests.

Will be obtained as outlined in section 7.1 - Trial Schedule of Events.

7.2.5.2 Experimental lab draws.

Will be performed at regularly scheduled clinic visits as outlined in section 2.2 - *Trial Schema/Diagram*. Peripheral blood mononuclear cells (PBMCs) will be isolated and flow cytometry will be used to quantify MDSCs and T cells.

- **Baseline immune response determination.** Subjects in the study will be asked to provide 40 mls of blood prior to initiating treatment to evaluate baseline immune responses and immune cell frequencies.
- **Immune response monitoring.** Blood samples will be drawn prior to the administration of the 2nd and 4th doses of pembrolizumab and after the last dose of VESANOID for continued measurement of immune cell frequencies.
- **Cytokine analysis.** Up to 20 ml of plasma will be stored for up to five years following study completion for subsequent cytokine analysis.

7.2.5.3 Specimen Analysis

Functional assays will be performed to assess the ability of isolated MDSCs to suppress T cell responses.

- Determination of tumor-specific T cell response frequency. Peripheral blood mononuclear cells (PBMCs) will be isolated over a ficoll gradient and cells will be banked to analyze the frequency of MDSCs and T cells using flow cytometry as previously published. PBMCs will be used to determine the frequency of tumor-specific T cell responses by stimulating the cells with a mixture of peptides derived from known melanoma tumor antigens including NYESO, gp100, and tyrosinase as well as measuring IFN-gamma production by flow cytometry.
- **T cell suppression assay.** The remaining PBMC will be used to perform T cell suppression assays using magnetically separated MDSC populations, comparing the suppressive function of MDSCs throughout treatment. Any remaining MDSCs will be flash frozen and banked for biomarker studies analyzing the expression of known suppressive molecules by real-time quantitative PCR.

7.2.5.4 Cytokine analysis.

Multiplex cytokine array will be used for subsequent cytokine analysis. Concentration of cytokines related to the function of MDSCs (GM-CSF, VEGF, MIP-1 alpha, MIP-1 beta, IL-10, IL-6, and IL-8) and T cells (IFN-gamma, TNF-alpha, IL-1-beta, IL-2, IL-4, IL-5, IL-12p70, IL-17) will be analyzed.

7.2.5.5 Biomarker analysis.

When available, representative histologic slides from each patient's primary or metastatic melanoma will be procured and submitted to QualTek for PD-L1 analysis. Correlations between baseline PD-L1 staining and MDSC assessments, progression free survival and clinical outcomes will be analyzed.

QualTek Molecular Laboratories [name] [contact]

